Part 5) Outcome Assessment. The primary outcome will be illicit opioid use at 1 week and 3 & 6 months after buprenorphine induction. Consistent with standard ATP practice, urine sample collection and analysis will be performed by Aspenti Labs (<https://www.aspenti.com/>), a clinical drug testing service which is open Monday to Friday 7AM-7PM and has multiple locations throughout Vermont. Urine specimens will be collected under observation of same-sex staff and analyzed for opioids (buprenorphine, methadone, oxycodone, hydrocodone, hydromorphone, heroin, fentanyl) and other drugs (cocaine, amphetamines, benzodiazepines, cannabinoids) via enzyme multiplied immunoassay. Missing urine specimens will be considered positive for illicit opioids, consistent with an intent-to-treat approach. Additional outcomes will include self-reported illicit opioid or other (non-opioid) drug use, treatment enrollment status and behavioral questionnaires (i.e. the GPRA Client Outcome Measures questionnaire to track self-reported drug-use and life conditions). The Treatment Effectiveness Assessment (TEA)⁴³ will be included at 1 week, 3 months and 6 months to track patient perception of treatment progress. Additional follow-up questions based on the PhenX toolkit are attached.

Retention. Participating in OUD treatment has health advantages for the participants which is a motivation to remain in the study. Participants will receive a \$25 gift card after answering questionnaires in Step 11. In addition, as an incentive to provide a urine sample and answer questions at follow-up, participants will receive a \$25 gift card for answering questions by phone and a \$50 gift card for a urine sample at each of the three outcome time points completed (i.e. 1 week, 3 and 6 months post randomization). In total, participants can earn up to \$250 for their participation in the study. To avoid altering the motivation to stay in MAT, participants will earn payment for providing the urine samples and answering questions at each of the 3 follow-up time points, regardless of whether they are currently in treatment. Missing urine specimens will be considered positive for illicit opioids, consistent with an intent-to-treat approach.

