Follow up questionnaire (attached) based on PhenX drug use history toolkit takes approximately 105 minutes to complete TEA takes approximately 5 minutes to complete

The GPRA Client Outcome Measures questionnaire takes approximately 30 minutes to complete.

Baseline questionnaires will be administered on an iPad by the EMRAP staff or the study RA in patient care areas or by phone.

At 1 week, 3 months and 6 months, questionnaires will be administered by the study RA by phone. Participants may be contacted in advance by text or email to arrange a time for the call that is convenient for the participant.

Questionnaires will be labelled with the participant's unique study ID number and stored separately from identifiable information (e.g. name, address, phone number etc).

Statistical Considerations: Delineate the precise outcomes to be measured and analyzed. Describe how these results will be measured and statistically analyzed. Delineate methods used to estimate the required number of subjects. Describe power calculations if the study involves comparisons. Perform this analysis on each of the primary and secondary objectives, if possible.

200 hundred individuals will be recruited to the study over the course of 3 years.

The primary outcome measure will be illicit opioid use at 1 week and 3 & 6 months.. Group differences (i.e. with or without the MAT bridge clinic) in opioid use will be assessed by logistic regression at each of the three time points. A power analysis using G*Power50 indicates that a medium effect size, e.g. 0.3, related to the comparison of illicit opioid use in the experimental and control groups will be correctly identified with a power of 0.93 in a total sample of 200 individuals. Statistical tests will be performed in SPSS Statistics for Windows, Version 21.0. (Armonk, NY: IBM Corp). Logistic regression will be one-tailed with significance defined as $p < 0.05$.

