Risks/Benefits: Describe any potential or known risks. This includes physical, psychological, social, legal or other risks. Estimate the probability that given risk may occur, its severity and potential reversibility. If the study involves a placebo or washout period, the risks related to these must be addressed in both the protocol and consent. Describe the planned procedures for protecting against or minimizing potential risks and assess their likely effectiveness. Where appropriate, discuss plans for ensuring necessary medical or professional intervention in the event of adverse effects to the subjects. Discuss the potential benefits of the research to the subjects and others. Discuss why the risks to the subjects are reasonable in relation to the anticipated benefits to subjects and others. Discuss the importance of the knowledge gained or to be gained as a result of the proposed research and why the risks are reasonable in relation to the knowledge that reasonably may result. If there are no benefits state so.

Risks

Identifiable Information. Information that uniquely identifies individuals will be collected from participants. This will include name, phone number, email, and address to facilitate contact with the participant at study follow-up points (i.e. 1 week, 3 months, 6 months). This information will be kept separate from other study materials, which will be coded with a subject number based on order of entry into the study.

Demographic, Behavioral and Drug Use Information. Demographic information including age, sex, marital status, and occupation will be collected. Opioid Use Disorder will be assessed with the 15 minute Mini-International Neuropsychiatric Interview (MINI). Opioid use history (e.g. onset, duration of use, route of administration) will be assessed with the opioid related items on the Pattern of Substance Use -Adult questionnaire in the PhenX toolkit (<https://www.phenxtoolkit.org/index.php?pageLink=browse.protocoldetails&id=510302>). In addition, the Addiction Severity Index-Lite CF (ASI-Lite), the 12-item Short Form Health Survey (SF-12), the Treatment Effectiveness Assessment (TEA)43 and the Vermont Treatment Needs Questionnaire (TNQ) interviews will be conducted.

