Clinical support for withdrawal will be provided by addiction psychiatrists at the ATP. Participants who receive ED-initiated buprenorphine treatment are guaranteed placement in the ATP. The ATP team includes two fellowship-trained addiction psychiatrists, one general psychiatrist, and one family

physician who are all experienced in treating OUD, as well as resident and fellow trainees from psychiatry, family medicine, and internal medicine, and licensed professionals in nursing, alcohol and drug counseling, mental health counseling and clinical social work. The staff is experienced in providing MAT to patients in all phases of treatment, in diverse settings and across levels of acuity, as well as in educating, training and supporting colleagues with varying levels of experience, training and comfort in addictions treatment. The ATP was selected by the State of Vermont to lead a state-wide Learning Collaborative Project to provide training and education to MAT practices throughout the state of Vermont.

Participant data will be coded to protect privacy. Each patient will be assigned a unique identification number. The list of participant names and identification numbers will be kept in a locked file cabinet separate from the database. Access to the computerized data system is carefully protected by a secured password entry system. Participants will be made aware of the various parties who will have access to their data in the informed consent document. Access to participants' data will be restricted to project investigators and other study staff on a need to know basis. Patient information, if reported, will be reported as group data. No patients will be individually identified.

To minimize risk of divulging confidential information regarding substance use or other illegal activities as well as other study information, strict attention to confidentiality will be maintained throughout every aspect of this research with standard policies and procedures, and protected by a Certificate of Confidentiality issued by NIH.

Individuals from vulnerable populations will not be included in the study.

Incidental findings will be reported to the participant by a study MD.

Potential Benefits

Participants enrolled in the study will either receive standard of care or buprenorphine MAT, which is the most effective current treatment for the disorder. Participants will be provided guaranteed access to treatment by specialized addiction psychiatrists at the ATP.

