A subject may decline to join the study, or may withdraw from the study at any time. Subjects declining consent or withdrawing from the study will have all data deleted, with the exception of the logs that document the destruction. The study code assigned to the subject will remain in the database with "voluntarily withdrawn from the protocol" as the only information retained about the subject (patient identifiers will not be saved except on the study master list).

Note: Participants are not required to test negative on urine drug tests at the assessment time points of 1 week, 3 months and 6 months. It is expected that many will test positive. Although drug tests are part of the ATP treatment program, this is independent of observational urine drug tests performed for the study at 1 week, 3 months and 6 months which will be used to determine the success of the ED-initiated intervention. Individuals who decline or withdraw from ATP services are not automatically withdrawn from the research study. Additionally, individuals who withdraw or are withdrawn from the study may continue to seek treatment services from the ATP. Participation or not in the study will not affect medical care provided by ED or the ATP.

Sources of Materials: *Identify sources of research material obtained from individually identifiable human subjects in the form of specimens, records or data. Indicate whether the material or data will be obtained specifically for research purposes or whether use will be made of existing specimens, records or data.*

Urine samples, Questionnaires, Medical History

DRUG AND DEVICE INFORMATION

Investigators are encouraged to consult the UVM Medical Center Investigational Pharmacy Drug Service ([name]) prior to finalizing study drug/substance procedures.

*Investigational Pharmacy Drug Service was consulted. They determined that IDS will not be involved in the current study because Suboxone is not be investigated as an IND. Rather, the research investigates a novel method to increase treatment enrollment with an already established use of Suboxone.

Drug (s)

Not applicable

Drug name – generic followed by brand name and common abbreviations. Availability – Source and pharmacology; vial or product sizes and supplier. If a placebo will be used, identify its contents and source. (attach investigational drug brochure)

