Subject Selection: *Provide rationale for subject selection in terms of the scientific objectives and proposed study design.*

Subjects will be screened for inclusion if they present to the ED with signs of opioid use disorder (i.e. self-report or symptoms consistent with the disorder) Symptoms consistent with the disorder include: presentation with acute overdose or symptoms consistent with opioid withdrawal (such as piloerection, diarrhea, tachycardia, cravings, and pupillary dilation), and EMS use of naloxone on scene or en route to the hospital, patients with abscesses, especially in the antecubital fossa and other areas consistent with injection drug use and patients with a history of endocarditis.

Vulnerable Populations: *Explain the rationale for involvement of special classes of subjects, if any. Discuss what procedures or practices will be used in the protocol to minimize their susceptibility to undue influences and unnecessary risk (physical, psychological, etc.).*

Not applicable

Number of Subjects: *What is the anticipated number of subjects to be enrolled at UVM/UVM Medical Center and in the case of a multi-center study, with UVM/UVM Medical Center as the lead, the total number of subjects for the entire study.*

We expect to enroll 140 participants at UVMMC and 200 participants in total.

Inclusion/Exclusion Criteria: Eligibility and ineligibility criteria should be specific. Describe how eligibility will be determined and by whom. Changes to the eligibility criteria at a later phase of the research have the potential to invalidate the research.

Inclusion Criteria:

- Present to the UVMMC Emergency Department (and later after IRB review the Emergency Departments at Central Vermont Medical Center and Porter Medical Center)
- Endorse criteria for Opioid Use Disorder (OUD) as defined by the DSM-V
- Over the age of 18

Exclusion Criteria:

- Non-english speaking
- Current participation in an alternate treatment program for OUD (except recent release from correctional facility or residential treatment program and does not have a current prescription),
- Inability to communicate
- Altered mental status
- Suicidality
- Medical extremis or medical issue requiring admission
- Prisoners
- History of Suboxone injection in the past year
- Hepatic impairment

Inclusion of Minorities and Women: Describe efforts to include minorities and women. If either minorities or women are excluded, include a justification for the exclusion.

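### Withdrawal from the study deletes urine results already obtained, so an observed negative at 1 week or 3 months is later either scored positive or lost, and the plan does not say which

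*Combined protocol and SAP*

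**What the plan says.** Three parts of the combined protocol and SAP bear on this.

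- **Deletion.** Withdrawal Procedures states: "Subjects declining consent or withdrawing from the study will have all data deleted, with the exception of the logs that document the destruction". What stays in the database is the study code, with a note of voluntary withdrawal "as the only information retained about the subject"; identifiers stay only on the study master list.
- **Missing specimens.** Objectives, Part 5) Outcome Assessment (twice) and Biological samples all carry the same rule: "Missing urine specimens will be considered positive for illicit opioids, consistent with an intent-to-treat approach".
- **Analysis.** Statistical Considerations says: "Group differences (i.e. with or without the MAT bridge clinic) in opioid use will be assessed by logistic regression", at each of 1 week, 3 months and 6 months, one-tailed at 0.05. It defines no analysis set, no handling of withdrawn participants and no sensitivity analysis.

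The scope of deletion is limited by a note under Withdrawal Procedures: "Individuals who decline or withdraw from ATP services are not automatically withdrawn from the research study". Only withdrawal from the research itself triggers it.

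**The concern.** The missing-specimen rule is written for samples that were never given. The deletion rule creates a different case: a sample that was given, tested and reported, and then removed. Take a participant who is negative at 1 week and at 3 months and withdraws in month 4. If the deleted results count as missing, two observed negatives enter the primary analysis as positives. If the participant is left out, the analysis no longer includes everyone enrolled. Either is worse than analysing the result that was observed.

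The direction of the error depends on the unstated choice. Scoring deleted results positive makes the group with more withdrawals look worse. Leaving them out makes that group look better if people who are using opioids withdraw more often. The choice could be made after the data are seen, and deletion rules out a later check of how much it mattered.

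**Working it through.** The plan contains no withdrawal rate and no figure on this point to reproduce. Its stated power of 0.93 does not bear on the question.

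**Which time points are exposed**

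| Time point | Can an observed result be deleted? |
|---|---|
| 1 week | Yes, by any later withdrawal |
| 3 months | Yes, by withdrawal after that sample |
| 6 months | Only by withdrawal after the last scheduled assessment |

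Someone who withdraws before 6 months has no 6-month sample and is scored positive with or without deletion. Under the scored-positive reading, month 6 is therefore essentially unaffected. Under the left-out reading, such a person disappears from month 6 as well.

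**Inputs**

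- From the documents: one-tailed 0.05. Number of Subjects says: "We expect to enroll 140 participants at UVMMC and 200 participants in total". UVMMC participants go to the bridge clinic, so the groups are 140 (bridge) and 200 − 140 = 60 (referral).
- Assumed: everyone gives a 1-week sample; the true positive rate is p = 0.50 in both groups; a share w of each group withdraws later. This is the most exposed case.

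**Method.** Exact enumeration over both binomial counts, with a one-tailed Wald test of the log odds ratio in the direction that favours the bridge group. If results are kept, the false-positive rate is 4.9%.

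**Deleted and scored positive, withdrawal unrelated to the result.** The analysed rate is p + w(1 − p).

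| w, bridge vs referral | Expected withdrawals | Analysed rates | Bridge − referral | False-positive rate |
|---|---|---|---|---|
| 1% vs 3% | 1.4 vs 1.8 | 50.5% vs 51.5% | −1.0 points | 6.4% |
| 2% vs 6% | 2.8 vs 3.6 | 51.0% vs 53.0% | −2.0 points | 8.2% |
| 5% vs 10% | 7 vs 6 | 52.5% vs 55.0% | −2.5 points | 9.2% |
| 5% vs 15% | 7 vs 9 | 52.5% vs 57.5% | −5.0 points | 15.8% |

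Example: 0.50 + 0.15 × 0.50 = 0.575. The true difference is zero in every row.

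**Deleted and left out.** If withdrawal is unrelated to the result, the comparison is unbiased and only sample size is lost. If only positives withdraw, the rate is (p − w)/(1 − w). At 5% vs 15% that gives (70 − 7)/(140 − 7) = 63/133 = 47.4% and (30 − 9)/(60 − 9) = 21/51 = 41.2%. The difference is +6.2 points and the rejection rate is 0.8%. The error now runs against the bridge group.

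**Power when there is a true effect** (assumed 40% bridge vs 60% referral)

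- Results kept: 83%.
- Equal 10% withdrawal: 76% if scored positive (46% vs 64%); 80% if left out (n = 126 and 54).
- Withdrawal 15% bridge, 5% referral, scored positive: 0.40 + 0.15 × 0.60 = 49% vs 0.60 + 0.05 × 0.40 = 62%; power 52%.

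**Leverage of one person.** One negative changed to positive moves the rate by 1/60 = 1.7 points in the referral group and 1/140 = 0.7 points in the bridge group.

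**The case against.** The strongest reply is that the missing-equals-positive rule appears four times, and its natural reading covers anyone with no result on file. If so, there is a gap to confirm rather than two rules in contradiction. That is fair. It does not remove the problem, because that reading scores a verified negative as positive.

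The second reply is that formal withdrawals may be rare. Leaving the bridge clinic does not count, a missed contact is not a withdrawal, and follow-up is paid whether or not the participant is in treatment. This stands. At the lowest rates shown the inflation is modest (6.4% against 4.9%), and every rate is assumed. The left-out example is severe: it has 9 of 30 referral positives (30%) withdrawing and no negatives.

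A reader might also infer that a withdrawn participant's group is lost, so that scoring is impossible. Group follows the enrolling hospital, and hospital is not among the items said to be kept. Study materials are "coded with a subject number based on order of entry into the study", and of the master list the plan says: "The list of participant names and identification numbers will be kept in a locked file cabinet separate from the database". But the contents of the destruction logs are not described, and the hospital might be traced through the master list. Only UVMMC is enrolling so far, with procedures at the other two hospitals still to come by amendment. Loss of group is a possibility to close off, not something the documents establish.

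Lastly, deletion on withdrawal is a defensible privacy choice for people disclosing illegal drug use. That is a real cost of changing it.

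**Conclusion.** The point holds for results at 1 week and 3 months. The protocol orders the destruction of valid primary-outcome data and leaves open whether the participant is then scored positive or omitted.

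A reader might infer that all three primary time points are corrupted. The documents do not support that under the scored-positive reading, because a 6-month result can be deleted only after follow-up has ended. Nor do they support treating clinic drop-out as a trigger for deletion.

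The size is illustrative. Under the stated assumptions the false-positive rate runs from 6.4% (1% vs 3% withdrawal) to 15.8% (5% vs 15%), against 4.9% with results kept. Equal withdrawal unrelated to the result produces no false signal, only some loss of power. The change is worth making because it costs little and deletion cannot be undone, not because a large bias has been shown.

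**What to change.** Replace the deletion sentence under Withdrawal Procedures with text to this effect:

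> Withdrawal stops further contact and data collection. Urine results obtained before withdrawal are kept in coded form and analysed at their time point; specimens due after withdrawal are missing and scored positive. Study code and enrolling hospital are kept for every enrolled participant. If a participant asks in writing for deletion, or enrolled under a consent form that promised it and does not re-consent, only code and hospital are kept; the participant is scored positive in the primary analysis and left out in a sensitivity analysis. Withdrawals and deletions are reported by group.

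The deletion route can still override an observed negative. It is confined to people who ask for it or were promised it, its scoring is fixed in advance, and the sensitivity analysis shows whether it matters.

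Cost: a protocol and consent-form amendment with IRB review, and no added visit, sample or payment. UVMMC is already enrolling. The consent form is not among the documents reviewed, so what current participants were promised must be checked before deciding who needs re-consent. The downside is less data removal for people with sensitive drug-use records, partly offset by coding and the Certificate of Confidentiality described under Protections Against Risks.
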